2.2 Background

ABP 501 is Amgen's biosimilar product to Humira® (adalimumab). ABP 501 is a tumor necrosis factor (TNF) blocker (a recombinant human IgG1 monoclonal antibody) indicated for treatment of chronic inflammatory conditions that include rheumatoid arthritis, juvenile idiopathic arthritis, psoriatic arthritis ankylosing spondylitis, adult Crohn's disease and ulcerative colitis, plaque Psoriasis (Ps). Please refer to prescribing information of the respective products (AMJEVITA™, AMGEVITA®). The new ABP 501-HCF (mg/mL) currently under development has no changes to the active substance, conditions of use, dosing regimen, or route of administration. The ABP 501-HCF contains 2 of the same excipients (sucrose and polysorbate 80) as the marketed ABP 501 but uses an based formulation compared to an acetate based formulation used for ABP 501. Refer to ABP 501 Investigator's Brochure for details and plans related to ABP 501- HCF.

mg/mL concentration formulation is approved and marketed for the adalimumab (US) reference product.

2.3 Benefit/Risk Assessment

mg) and dose regimens of both investigational products proposed in this study are consistent with the ABP 501 and Humira® products prescribing information for patients with plaque Ps. Thus, the risks and benefits of ABP 501-HCF are expected to be similar to those of adalimumab (reference product). More detailed information about the expected benefits, risks, and potential adverse reactions to ABP 501 can be found in the ABP 501 Investigator's Brochure.

present in the new ABP 501-HCF, to be used in this study, is generally recognized as a naturally occurring substance that is safe for humans and the amount of in the maximum ABP 501-HCF dose is below what is currently approved for other marketed SC administered products. No clinically meaningful differences in the safety or local, injection site tolerability of ABP 501-HCF (mg/mL) compared with adalimumab (mg/mL formulation)

Clinical Study Protocol: 20200497

Final 1.0 Date: 03 Jun 2021 Page **21** of **87**

are expected. Of note, a risk assessment will be performed on an ongoing basis to evaluate the potential impact of coronavirus disease 2019 (COVID-19) on subjects. Risk mitigation measures, including COVID-19 related precautions and procedures (including severe acute respiratory syndrome coronavirus 2 [SARSCoV2] testing/screening) will be implemented based on the prevailing situation during study conduct, at the investigator's discretion and in accordance with local and institutional guidelines, as applicable.

2.4 Overall Benefit: Risk Conclusion

Considering the measures taken to minimize risk to subjects participating in this study, the potential risks identified in association with ABP 501-HCF, as well as switching between ABP 501-HCF and adalimumab (US), are justified by the anticipated benefits to subjects with moderate to severe Ps. On the basis of the available nonclinical and clinical data, and prior knowledge of ABP 501 mg/m mL and adalimumab mg/m mL and mg/m mL (Humira®), the risk-benefit profile of ABP 501 mg/m mL (ABP 501-HCF) is judged acceptable for the proposed clinical study.

Final 1.0 Date: 03 Jun 2021 Page **22** of **87**

3 Objectives and Endpoints

Table 3-1. Objectives and Endpoints

Objectives	Endpoints
Primary Objective: To demonstrate similarity of PK in subjects after multiple switches between adalimumab and ABP 501, compared to subjects receiving continued-use of adalimumab.	Primary Endpoints: Pharmacokinetic parameters: • AUC _{tau} between week 28 and week 30 • C _{max} between week 28 and week 30.
Secondary Objective: To assess the efficacy, safety, and immunogenicity in subjects after multiple switches between ABP 501 and adalimumab compared with subjects receiving continued-use of adalimumab.	Secondary Endpoints: Pharmacokinetic related Endpoints: t _{max} between week 28 and week 30. Ctrough between week 14 and week 28. Efficacy related Endpoints: PASI percent improvement from baseline (day 1) to week 30. PASI 75 response at week 30. PASI 90 response at week 30. PASI 100 response at week 30. Safety related Endpoints: Treatment-emergent adverse events and serious adverse events, post randomization. Events of interest, post randomization. Immunogenicity-related Endpoints: Incidence of ADAs, post randomization

ADAs = antidrug antibodies; AUC_{tau} = area under the curve from time 0 over the dosing interval; C_{max} = maximum concentration; C_{troug} =: trough concentration; PK = pharmacokinetic(s); PASI: Psoriasis Area and Severity Index; t_{max} = time of maximum concentration.

Clinical Study Protocol: 20200497 Final 1.0 Date: 03 Jun 2021

4 Study Design

4.1 Overall Design

This is a randomized, double-blind, phase 3 study in adult subjects with moderate to severe Ps. This study is planned to be conducted globally at study centers including but not limited to North America and Europe.

The total duration of study participation for each subject will be about 36 weeks, with up to 4 weeks for screening and approximately 32 weeks after the first investigational product administration.

Table 4-1. Investigational Product Groups

Reference Group Adalimumab Continued-use Group	Continued-use of adalimumab administered by SC injection using prefilled syringes at a dose of mg (2 x mg loading dose) on week 1/day 1 and mg administered 1 week later at week 2/day 8, then at 2 weeks interval at week 4, week 6, week 8, and week 10. Subsequent dosing will be at mg every 2 weeks thereafter up to and including week 28.	
Test Group Switching Group	Switching group with adalimumab administered by SC injection using prefilled syringes at a dose of mg (2 x mg loading dose) on week 1/day 1 and mg administered 1 week later at week 2/day 8, then at 2 weeks interval at week 4, week 6, week 8, and week 10. • At week 12, subjects will be switched to ABP 501 and administered ABP 501 mg SC on weeks 12 and 14. • At week 16, subjects will be switched back to adalimumab and administered adalimumab mg SC on weeks 16 and 18. • At week 20, subjects will then be switched to ABP 501 and administered ABP 501 mg SC on weeks 20, 22, 24, 26, and with last dose on	

SC = subcutaneous.

The study is composed of two periods. A lead-in period of treatment with adalimumab (weeks: 1 to 12) followed by a randomized two parallel arm period (weeks: 12 to 32). Subjects will receive an initial 6 doses of adalimumab on day 1/week 1 (mg loading dose), 1 week later on day 8/week 2 (mg), then at 2 weeks interval on week 4, week 6, week 8, and week 10 (mg), administered subcutaneously (SC). At week 12, subjects with Psoriasis Area and Severity Index (PASI) ≥ 50 (PASI 50) response will be randomized to either the continued-use group or switching group in a 1:1 ratio, stratified by geographic region and prior biologic use at baseline (week 1/day 1, yes vs. no). Subjects achieving less than PASI 50 response at week 12 visit will be considered non-responders and will be discontinued from the study at week 12. These subjects will be asked to complete End of Study (EOS) Visit procedures. Subjects randomized to the continued-use group will continue on adalimumab

Q2W with last dose at week 28. Subjects randomized to the switching group will switch to ABP 501 Q2W at week 12 (dosed week 12 and week 14), then back to adalimumab Q2W at week 16 (dosed week 16 and week 18), and again to ABP 501 Q2W at week 20, (dosed week 20, week 22, week 24, week 26, and with last dose of ABP 501 at week 28).

All enrolled subjects not randomized at week 12 will be considered lead-in failures and the lead-in failure reason will be documented.

An EOS Visit will be conducted at week 32.

4.2 Scientific Rationale for Study Design

The current study is designed to demonstrate that the risk in terms of safety or diminished efficacy of switching between ABP 501 (a proposed interchangeable biosimilar product) and adalimumab (a reference product) is not greater than the risk of using adalimumab without such switch.

A dedicated switching study approach has been selected, as outlined in the US FDA guidance (Guidance for Industry: Biosimilars: Considerations in Demonstrating Interchangeability with a Reference Product, May 2019).

This study is designed to assess whether switching between adalimumab (reference product) and ABP 501-HCF (three switches with the last switch from adalimumab to ABP 501-HCF) will result in differences in PK or immunogenicity profiles, when compared to continued therapy with adalimumab (reference product). The C_{max} and AUC_{tau} at the end of multiple switching between investigational products were chosen as co-primary PK study endpoints.

The FDA guidance provides recommendations to conduct clinical switching studies in relevant patient population rather than in healthy volunteers. Population of subjects with moderate to severe plaque psoriasis was thus selected for this study, as it offers a sensitive model to detect potential differences with regard to immunogenicity, PK, safety, and efficacy (Guidance for Industry: Biosimilars: Considerations in Demonstrating Interchangeability with a Reference Product, May 2019) in a repeat dose setting.

4.2.1 Subject Input into Design

Not applicable.

4.3 Justification for Dose

The doses used in this study include both the mg initial loading dose, followed by every other week starting one week after initial dose and the mg Q2W dose, all of which are used as per the label (AMJEVITA™ USPI, June 2019). See Section 6.7 for dose modifications.

4.4 End of Study Definition

A subject is considered to have completed the study if he/she has completed all phases of the study including an EOS Visit or the last scheduled procedure shown in the Schedule of Assessments (Table 1-1). An EOS visit will be performed for subjects who are prematurely discontinued. All procedures listed under EOS visit must be completed for subjects who are prematurely discontinued.

The EOS is defined as the date of the last visit of the last subject in the study or last scheduled procedure shown in the Schedule of Assessments (Table 1-1) for the last subject in the study globally.

5 Study Population

The study population will consist of subjects with moderate to severe Ps (See Section 4.2 for details on rationale). Subjects (or legally acceptable representative) must be able to provide written consent and subjects must meet all the inclusion criteria and none of the exclusion criteria.

Approximately 414 subjects will be enrolled. Randomization will be stratified by prior biologic use for psoriasis at baseline (week 1/day 1, yes vs. no) and geographic region. Subjects with prior biologic use for psoriasis will be capped at 50% of the total enrolled subjects.

The number of subjects enrolled may be adjusted during the study with the actual lead-in failure rate seen to ensure approximately 342 subjects will be randomized at week 12.

5.1 **Inclusion Criteria**

Subjects cannot be enrolled before all the inclusion criteria (including test results) are confirmed. Subjects are eligible to be included in the study only if all of the following criteria apply:

1. Subject is male or female and is ≥ 18 and ≤ 75 years of age inclusive, at the time of enrollment.

Clinical Study Protocol: 20200497

Final 1.0 Date: 03 Jun 2021 Page **26** of **87**

2. Subject has moderate to severe Ps (with or without psoriatic arthritis) for at least 6 months and has stable disease for at least 2 months (eg, no morphology changes or significant flares of disease activity in the opinion of the investigator).

- 3. Subject has a score of PASI ≥ 12, involvement of ≥ 10% body surface area (BSA) and static Physician's Global Assessment (sPGA) ≥ 3 at screening and at baseline.
- 4. Subject is a candidate for phototherapy or systemic therapy, when other systemic therapies are clinically less appropriate.
- 5. Female subject (except if postmenopausal or surgically sterile, definitions outlined in Section 10.2): a negative serum pregnancy test during screening and a negative urine pregnancy test at baseline.
- 6. Subject or legally acceptable representative is capable of giving signed Institutional Review Board (IRB)/Independent Ethics Committee (IEC) informed consent.
- 7. Subject has no known history of latent or active tuberculosis. Subject must meet any 1 of the following 3 criteria:
 - Subject has a negative test for tuberculosis during screening, defined as either:
 - Negative purified protein derivative (PPD); < 5 mm of induration at
 48 hours to 72 hours after test is placed, or
 - Negative QuantiFERON®/T-spot® test.
 - Subject with a positive PPD test and a history of Bacillus Calmette Guerin (BCG) vaccination is allowed with a negative QuantiFERON®/T-spot® test.
 - Subject with a positive PPD test (without a history of BCG vaccination) or subject with a positive or indeterminate QuantiFERON®/T-spot® test is allowed if he/she has all of the following:
 - No symptoms per tuberculosis worksheet provided by the sponsor, Amgen Inc.
 - Documented history of adequate prophylaxis initiation prior to receiving investigational product in accordance with local recommendations.
 - No known exposure to a case of active tuberculosis after most recent prophylaxis.
 - No evidence of active tuberculosis on chest radiograph taken within 3 months prior to the first dose of investigational product and read by a qualified radiologist/specialist.

Final 1.0 Date: 03 Jun 2021 Page 27 of 87

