5.5 Screen Failures

Screen failures are defined as subjects who consent to participate in the clinical study but are not subsequently enrolled to the study. A minimal set of screen failure information is required to ensure transparent reporting of screen failure subjects to meet the Consolidated Standards of Reporting Trials publishing requirements and to respond to queries from regulatory authorities. Minimal information includes demography, reason for screen failure (eg, eligibility requirements failed), and any serious adverse events. Data for subjects who have screen failed will not be entered in the eCRF.

If a subject has not met all eligibility criteria at the end of the screening period, the subject will be registered as a screen failure. Individuals who do not meet the criteria for participation in this study (screen failure) may be rescreened. Rescreened subjects should be assigned the same

subject identification number as for the initial screening. Laboratory assessments used to determine subject eligibility may be repeated during the screening period before the subject is considered a screen failure. Screen failed subjects may be rescreened up to 2 times at the investigator's discretion (ie, a total of 3 screens including initial screening). If screening procedures cannot be completed within 28 days before day 1, the subject will be considered a screen failure but may be eligible for rescreening. These subjects can be rescreened under the same ICF if rescreening and enrollment occurs within 30 days of initial consent date. If it is longer than 30 days from the initial consent date, the subject will need to be re-consented and all screening procedures need to be repeated.

6 Investigational Product

Investigational product is defined as any investigational intervention(s), marketed product(s), placebo, or medical device(s) intended to be administered to a study subject according to the study protocol.

The investigator must ensure that the investigational product will be used only in accordance with the protocol. Study treatments and investigational product are described in Table 6-1.

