8.2.3 Tuberculosis Testing

A tuberculosis test will be performed at screening by PPD or QuantiFERON®/T-spot® test. Further tuberculosis tests could be performed at the discretion of the investigator and according to local practice. Purified protein derivative tests will be performed locally, and QuantiFERON®/T-spot® tests will be performed by the local or central laboratory. Subjects with positive or indeterminate QuantiFERON®/T-spot® test, positive PPD may be eligible based on the sponsor's tuberculosis assessment worksheet and the other criteria listed in inclusion criterion 7.

Final 1.0 Date: 03 Jun 2021 Page **46** of **87**

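### When a subject has both a PPD and an IGRA result at screening, inclusion criterion 7 lets one negative result bypass the prophylaxis and exposure conditions for three patterns that its own third limb names

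*Protocol*

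**What the plan says.** Criterion 7 in Protocol Section 5.1 opens by barring a known history of latent or active tuberculosis. It then states: "Subject must meet any 1 of the following 3 criteria". The three limbs are:

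- **Limb 1:** "Subject has a negative test for tuberculosis during screening, defined as either" a negative PPD or a negative QuantiFERON/T-spot (IGRA). Nothing is said about a second result.
- **Limb 2:** "Subject with a positive PPD test and a history of Bacillus Calmette Guerin (BCG) vaccination is allowed with a negative QuantiFERON®/T-spot® test".
- **Limb 3:** a subject with a positive PPD and no BCG history, "or subject with a positive or indeterminate QuantiFERON®/T-spot® test is allowed if he/she has all of the following". Four conditions follow. Two are no symptoms on the sponsor's worksheet and no active tuberculosis on a recent chest radiograph. The third concerns preventive treatment: "Documented history of adequate prophylaxis initiation prior to receiving investigational product in accordance with local recommendations". The fourth concerns contact with the disease since that treatment: "No known exposure to a case of active tuberculosis after most recent prophylaxis".

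On testing, Section 8.2.3 says: "A tuberculosis test will be performed at screening by PPD or QuantiFERON®/T-spot® test". It allows further tests at the investigator's discretion. It adds that subjects with a positive or indeterminate result may be eligible on the worksheet together with the rest of criterion 7. Table 1-1 schedules a chest radiograph at screening, and its worksheet footnote calls for the worksheet after any positive or indeterminate result.

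**The concern.** The limbs are alternatives, so meeting limb 1 is enough. Limb 1 looks only for one negative result. If a subject has two results and they disagree, the negative one satisfies limb 1 and the conditions in limb 3 never come into play, even though limb 3 describes that subject's other result.

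Two results are foreseeable. Limb 2 cannot be applied without both a PPD and an IGRA, and Section 8.2.3 permits further tests. Footnote d of Table 1-1 calls for an IGRA or local equivalent, while Section 8.2.3 accepts a PPD, so a site that starts with a PPD may end up holding both.

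What is at stake is subject safety. The study drug is a TNF blocker given at up to 15 dosing visits: 6 in the lead-in (weeks 1, 2, 4, 6, 8, 10) plus 9 from week 12 to week 28. Section 6.7 notes that elimination takes months after stopping, so an entry error is not quickly undone. The sponsor chose to require prophylaxis before dosing for these results, and the text should enforce that choice.

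**Working it through.** The plan states no figure on this point. The check is a listing of result patterns, not of subjects.

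**Inputs (criterion 7).**

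- Limb 1 is met if PPD is negative OR IGRA is negative.
- Limb 2 is met if PPD is positive AND there is a BCG history AND IGRA is negative.
- Limb 3 names a subject if PPD is positive without BCG history, OR IGRA is positive or indeterminate.
- Entry requires limb 1 OR limb 2 OR limb 3 with all four of its conditions.

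**Step 1: one test only.** PPD alone gives 2 results x 2 BCG histories = 4 cases. IGRA alone gives 3 results x 2 BCG histories = 6 cases. Of these 4 + 6 = 10 cases, none both meets limb 1 and is named by limb 3. Bypass: 0 of 10.

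**Step 2: both tests, text as it stands.** Three PPD/BCG states x three IGRA results = 9 cells.

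| PPD / BCG | IGRA negative | IGRA positive | IGRA indeterminate |
|---|---|---|---|
| PPD negative | Limb 1 | **Limb 1 and limb 3** | **Limb 1 and limb 3** |
| PPD positive, BCG | Limbs 1 and 2 | Limb 3 | Limb 3 |
| PPD positive, no BCG | **Limb 1 and limb 3** | Limb 3 | Limb 3 |

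- Limb 1 is met in 3 + 1 + 1 = 5 cells.
- Limb 2 is met in 1 cell, which limb 1 already covers. No cell depends on limb 2, so it is redundant.
- Limb 3 names 2 + 2 + 3 = 7 cells.
- Limbs 1 and 3 overlap in 5 + 7 - 9 = 3 cells (every cell is in at least one of the two). These are the cells in bold.

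**Step 3: which conditions are lost in those 3 cells.** Take limb 3's four conditions in turn.

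- *Worksheet:* still completed after any positive or indeterminate result (Table 1-1), and named in Section 8.2.3 as a basis for eligibility.
- *Chest radiograph:* still scheduled for all subjects at screening. A film showing active disease would engage exclusion 3.
- *Prophylaxis started:* required nowhere else.
- *No known later exposure:* required nowhere else.

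So 2 of the 4 conditions have no other rule behind them.

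**Step 4: after the rewording given under the fix.** Limb 1 covers 1 cell (both negative), limb 2 covers 1 (PPD positive with BCG, IGRA negative) and limb 3 covers 7. Then 1 + 1 + 7 = 9, with no overlap. Cells that can enter without limb 3 fall from 5 to 2, and the 3 removed are exactly the bold ones.

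**The case against.** The best defence rests on Section 8.2.3. It ties the eligibility of test-positive subjects to the worksheet and to the remainder of criterion 7, and within that criterion the worksheet appears only in limb 3. One can therefore read Section 8.2.3 as sending every positive result to limb 3, with limb 2 as the BCG exception. The redundancy of limb 2 points the same way, since drafters rarely include a limb meant to do nothing. This makes the intended meaning fairly clear. It does not supply an operative rule: the cross-reference is to criterion 7 as a whole, which is governed by its own any-one connector, and no sentence in either document ranks discordant results. The opening bar on known tuberculosis does not close the gap. If a new positive screening result counted as known history, limb 3 could admit nobody.

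Three other parts of the defence stand. The reach is narrow, because the plan calls for one test. Footnote d speaks of additional tests during the study, which gives less support for a second result before enrolment. And the remaining protections are real: radiograph, worksheet, and exclusions 3 and 11, although both exclusions turn on the investigator's opinion.

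A reader might also infer that a positive IGRA later repeated as negative is a further loophole. The documents do not support calling that a defect. Section 5.5 says: "Laboratory assessments used to determine subject eligibility may be repeated during the screening period before the subject is considered a screen failure". Which result then counts is a clinical choice for the sponsor, for positive and indeterminate first results alike.

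**Conclusion.** The point holds on the wording of criterion 7 and is limited to subjects with both a PPD and an IGRA result at screening. For 3 of 9 two-test patterns, all named in limb 3, a subject can enter without prophylaxis having started and without the check on later exposure. Limb 2 has no effect as written.

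The conclusion assumes that sites apply the any-one rule literally. Section 8 allows no waivers, but a site could still read the criterion as the drafters probably meant it.

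Two stronger inferences are not supported. One is that such subjects enter with no tuberculosis safeguards: the radiograph, the worksheet and exclusions 3 and 11 all remain. The other is that a material share of the trial, or its PK comparison, is affected: the documents give no rate of dual testing or discordance, so no subject count can be derived, and nothing links the point to the PK endpoints. It is a gap in a stated safety rule that should be closed because closing it is cheap.

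**What to change.** 1. Reword limb 1 to: *a negative PPD or negative QuantiFERON/T-spot, and no positive PPD and no positive or indeterminate QuantiFERON/T-spot result on the other test*.
2. Keep limb 2 as the only exception: PPD positive with BCG history and IGRA negative.
3. State that every other positive or indeterminate result goes to limb 3, whose four conditions stay as they are.
4. If an IGRA is repeated under Section 5.5, have the sponsor state one rule for which result counts and apply it identically in limbs 1 and 2. A bar on an earlier indeterminate result in limb 1 alone would treat a PPD-negative subject more strictly than a PPD-positive subject with BCG history.

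The cost is eligibility wording in an amendment. No test is added and entry is not loosened. A few subjects with discordant results would have to meet limb 3 before dosing, so they would be delayed or would fail screening.
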